## **2.5 DATA HANDLING CONVENTIONS**

Some general rules of data handling conventions are listed below.

### **2.5.1 General conventions**

In general, the baseline value of an analysis variable is defined as the last observation before or on the first dose of the treatment.

Last on-treatment value is defined as the value collected at or just prior to the last study drug intake.

#### ***Time from diagnosis***

Time from diagnosis (years) = (Date of informed consent - Date of diagnosis\*)/365.25

(\*) In case the month of diagnosis would be missing, it will be put equal to 01 JANUARY if the year of diagnosis equals the year of informed consent; it will be put equal to 01 JULY otherwise. In case the day of diagnosis would be missing, it will be put equal to 15 if the

consent and the diagnosis did not occur during the same month; it will be put equal to 1 otherwise.

### ***Demographic and baseline characteristics***

Age = Integer of ([date of informed consent - date of birth]/365.25)

### ***Medical history***

“Peripheral Arterial Disease” corresponds to at least one of the following conditions:

- Intermittent claudication.
- Peripheral revascularization procedure (angioplasty, stenting).
- Thrombolysis for PAD.
- Peripheral revascularization surgery (arterial bypass).
- Critical limb ischemia.

### ***Date of last dose of IMP***

The date of the last injection is equal to the last date of administration reported on injection administration case report form page, or missing if the last administration date is unknown.

### ***Renal function formulas***

The following formulas has been used for below parameter automatic calculation in the eCRF:

**eGFR** value will be derived using the MDRD equation:

eGFR (mL/min/1.73 m^2) = 175 x (Serum Creatinine converted in mg/dL)-1.154 x (Age)-0.203  
x (0.742 if Female) x (1.212 if African American)

**Creatinine Clearance** is calculated using the Cockcroft-Gault formula:

- If serum creatinine measured in **mg/dL**:  
$$\text{CrCl} = ([140-\text{age}] \times [\text{Weight in kg}] \times [0.85 \text{ if women}]) / (72 \times \text{Serum Creatinine in mg/dL}).$$
- If serum creatinine measured in **μmol/L**:  
$$\text{CrCl} = ([140-\text{age}] \times [\text{Weight in Kg}] \times [1.23 \text{ if men and 1.04 if women}]) / (\text{Serum Creatinine in } \mu\text{mol/L}).$$

### ***Lipid formulas***

**LDL-C** is calculated using the Friedewald formula (1) in all cases, ie, even in case TG are elevated (>400 mg/dL):

- $\text{LDL-C} = \text{Total-C} - \text{HDL-C} - (\text{TG}/2.17)$ , when all concentrations are expressed in mmol/L.
- $\text{LDL-C} = \text{Total-C} - \text{HDL-C} - (\text{TG}/5)$ , when all concentrations are expressed in mg/dL.  
In order to convert the result into mmol/L, divide by 39.

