## 7 SELECTION OF PATIENTS

### 7.1 INCLUSION CRITERIA

- I 01. Signed written informed consent.
- I 02. Age  $\geq 18$  years or legal age of majority at screening visit.
- I 03. Either A, B, C, D or E below and not adequately controlled with a maximally tolerated dose of statin\* with or without other lipid modifying therapy (LMT), all at stable doses for at least 4 weeks prior to the screening visit (Week -3).

**A. Patients suffering from heterozygous familial hypercholesterolemia\*\* (heFH) with LDL-C concentrations  $\geq 160$  mg/dL (4.14 mmol/L) despite treatment**

**B. Patients suffering from heFH with LDL-C concentrations  $\geq 130$  mg/dL (3.36 mmol/L) despite treatment and two or more CV risk factors among this list:**

- LDL-C  $> 250$  mg/dL (6.46 mmol/L) at the time of the FH diagnosis (before treatment),
- Family history of premature-onset CHD (first-degree male relative with onset before age 55 years; first-degree female relative with onset before age 65 years),
- Metabolic syndrome (cf. definition),
- HDL-C  $< 40$  mg/dL (1.03 mmol/L),
- Hypertension (BP  $> 140/90$  mmHg or drug treatment),
- Lp(a)  $\geq 50$  mg/dL (1.78  $\mu$ mol/L),
- Tendon xanthoma.

**C. Patients suffering from heFH with LDL-C concentrations  $\geq 130$  mg/dL (3.36 mmol/L) despite treatment and one of the following characteristics:**

- **established CHD or other CVD** (history of acute myocardial infarction, ischemic stroke, peripheral arterial disease, coronary or peripheral arterial revascularization, stable or unstable angina, transient ischemic attack, carotid artery stenosis  $\geq 50\%$ , aortic abdominal aneurysm),
- **drug treated type 2 diabetes mellitus or type 1 with target organ damage**,
- **family history of first or second degree relative with very premature onset CHD** (first or second degree male relative onset before age 45; first or second degree female relative onset before age 55).

**D. Non-FH patients suffering from established CHD or other CVD** (history of acute myocardial infarction, ischemic stroke, peripheral arterial disease, coronary or peripheral arterial revascularization, stable or unstable angina, transient ischemic attack, carotid artery stenosis  $\geq 50\%$ , aortic abdominal aneurysm) **and with LDL cholesterol concentrations  $\geq 130$  mg/dL (3.36 mmol/L).**

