Note that the original version of protocol included a post-treatment follow-up visit taking place 10 weeks after the last injection for patients who prematurely discontinued alirocumab for any reason as well as for those who switched to another LMT. For those patients who participated in the study under the original version of protocol, the EOT visit and the EOS visit did not occur at the same time (see [Section 1.5](#)).

The end of the study per patient is the last protocol planned visit or the resolution/stabilization of all serious adverse events (SAEs) and adverse events of special interest (AESIs), or death, whichever comes last.

During the screening and inclusion visits, it was checked that patients were not adequately controlled with a maximally tolerated dose of statin\* with or without other LMT, all at stable doses for at least 4 weeks prior to the screening visit and could be classified in at least one of the following groups to be included in the study:

- A. Patients suffering from heterozygous familial hypercholesterolemia (heFH) with LDL-C concentrations  $\geq 160$  mg/dL (4.2 mmol/L) despite treatment.
- B. Patients suffering from heFH with LDL-C concentrations  $\geq 130$  mg/dL (3.4 mmol/L) despite treatment and two or more cardiovascular (CV) risk factors among this list:
  - Baseline LDL-C  $> 6.46$  mmol/L (250 mg/dL) at the time of the familial hypercholesterolemia (FH) diagnosis (before treatment).
- Family history of premature-onset coronary heart disease (CHD)
  - CHD (first-degree male relative with onset before age 55 years; first-degree female relative with onset before age 65 years),
  - Metabolic syndrome (cf. definition in protocol),
  - High density lipoprotein cholesterol (HDL-C)  $< 1.03$  mmol/L (0.40 g/L),
  - Hypertension (blood pressure [BP]  $> 140/90$  mmHg or drug treatment),
  - Lp(a)  $\geq 0.50$  g/L (1.78  $\mu$ mol/L),
  - Tendon xanthoma.
- C. Patients suffering from heFH with LDL-C concentrations  $\geq 130$  mg/dL (3.4 mmol/L) despite treatment and one of the following characteristics:
  - **established CHD or other cardiovascular disease (CVD)** (history of acute myocardial infarction [MI], ischemic stroke, peripheral arterial disease [PAD], coronary or peripheral arterial revascularization, stable or unstable angina, transient ischemic attack, carotid artery stenosis  $\geq 50\%$ , aortic abdominal aneurysm),
  - **drug treated type 2 diabetes mellitus or type 1 with target organ damage**

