### 2.1.3 Efficacy endpoints

Efficacy endpoints include lipid parameters: calculated LDL-C, Total-C, HDL-C, TG, non-HDL-C. Total-C, HDL-C, TG will be provided by a local Laboratory. LDL-C will be calculated using the Friedewald formula [\(1\)](#) at all site visits (see [Section 2.5.1](#)). One of the most important limitations of the Friedewald formula is that it is not appropriate at TG concentrations >400 mg/dL, anyway and in order to simplify the computations this formula will be used regardless of the TG values. Non-HDL-C is calculated by subtracting HDL-C from the Total-C.

Unless otherwise specified, all lipid values (scheduled or unscheduled, fasting or not fasting) may be used to provide a value for the efficacy endpoints. All measurements, scheduled or unscheduled, fasting or not fasting, will be assigned to analysis windows defined in [Table 2](#) in order to provide an assessment from Week 4 to the end of the study.

The main efficacy endpoint will be the LDL-C at Week 12 (change from baseline). Nevertheless, all efficacy endpoints will be described at each time point.

For all post-baseline time points, the value used for the analyses at a given time point will be the value obtained within the corresponding analysis window. The baseline value is defined as the last available measurement obtained before the date of the first injection of alirocumab.

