### **2.1.3.2 Secondary efficacy endpoint(s)**

The main efficacy secondary endpoint will be:

- The percent change in calculated LDL-C from baseline to Week 12 (on-treatment estimand).

The key secondary efficacy endpoints will include:

- The proportion of patients reaching calculated LDL-C <100 mg/dL (2.59 mmol/L) at Week 12 (on-treatment estimand).
- The proportion of patients reaching calculated LDL-C <70 mg/dL (1.81 mmol/L) at Week 12 (on-treatment estimand).
- The proportion of patients with LDL-C <70 mg/dL (1.81 mmol/L) and/or ≥50% reduction from baseline in calculated LDL-C at Week 12 (on-treatment estimand).
- The percent change in non-HDL-C, total-C, HDL-C, TG from baseline to Week 12 (on-treatment estimand).

The other secondary efficacy endpoints will be:

- The proportion of patients who were up-titrated from 75 mg Q2W to 150 mg Q2W of alirocumab during the observational period based on investigator's judgment (on-treatment estimand).
- The proportion of patients who were down-titrated from 150 mg Q2W to 75 mg Q2W of alirocumab during the observational period based on investigator's judgment (on-treatment estimand).
- The reasons (ie, LDL-C threshold, AE) that triggered a down-titration or an up-titration of alirocumab (on-treatment estimand).
- The percent change in LDL-C from baseline over time, using all LDL-C values during the efficacy treatment period (on-treatment estimand) defined in [Section 2.3.1](#).
- The absolute change in calculated LDL-C (mg/dL and mmol/L) from baseline over time, using all LDL-C values during the efficacy treatment period (on-treatment estimand).
- The proportion of patients reaching calculated LDL-C <100 mg/dL (2.59 mmol/L) over time (on-treatment estimand).
- The proportion of patients reaching calculated LDL-C <70 mg/dL (1.81 mmol/L) over time (on-treatment estimand).
- The proportion of patients with calculated LDL-C <70 mg/dL (1.81 mmol/L) and / or ≥50% reduction from baseline in calculated LDL-C over time (on-treatment estimand).
- The percent change in non-HDL-C, total-C, HDL-C, TG from baseline over time (on-treatment estimand).
- The absolute change in non-HDL-C, total-C, HDL-C, TG (mg/dL and mmol/L) from baseline over time (on-treatment estimand).

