## 2.4 STATISTICAL METHODS

All statistical analyses will be descriptive and no formal statistical test will be performed.

Analyses will be performed overall and on some sub-groups of interest such as:

- Patients included in each of the risk groups at inclusion (see [Section 1.1](#)) enrolled patients who did not fulfill inclusion criterion I 03 will not be considered for this subgroup analysis. However, they will be part of the overall analysis.
- Patients with heFH / non-familial FH.
- Type 1 and Type 2 diabetes mellitus / patients without diabetes.
- Established CHD or other CVD (including patients suffering from progressive cardiovascular disease).

Results will be reported globally without regional subgroups.

The results per country if sample size is sufficient ( $\geq 30$ ), or by pooled countries if sample size is not sufficient ( $< 30$ ), will not be displayed in this Statistical Analysis Plan but it will be displayed in post-hoc analysis if it is necessary and asked by the medical countries affiliates.

*(Since some countries will include a small number of patients, the statistical results for these countries will have to be interpreted with caution. Likewise, some sub-groups might include a very small number of patients and the statistical results will have to be discussed when analysis will be displayed in post-hoc. Suggested pooled countries could be as follows: Denmark with Finland; Germany with Belgium; Slovakia with Czech Republic; and the last one, Slovenia with Hungary, Romania, and Greece).*

Final analysis will be performed after the global Data Base Lock.

Efficacy analysis, AEs analysis and demographics description will be displayed overall, and by the sub-groups of interest described above.

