#### **2.4.4.4 Additional efficacy analyses**

##### ***Occurrence of very low LDL-C level***

A LDL-C level <25 mg/dL (0.65 mmol/L) will be defined as very low. An alternative definition with a cut-off at 15 mg/dL (0.39 mmol/L) will also be used.

For each definition of very low LDL-C level, the number and percentage of patients who had a very low LDL-C level at least once during the observational period will be provided overall, by the LDL-C level at baseline (<70 mg/dL (1.81 mmol/L),  $\geq 70$  mg/dL and <100 mg/dL (2.59 mmol/L),  $\geq 100$  mg/dL and <130 mg/dL (3.37 mmol/L),  $\geq 130$  mg/dL and <160 mg/dL (4.14 mmol/L),  $\geq 160$  mg/dL) and by starting dose of alirocumab.

Among patients with a very low LDL-C level, the number and percentage of patients receiving each level of dose for alirocumab (75 mg and 150 mg) at the time of the corresponding LDL-C test will be provided. The time from the first injection of Alirocumab to the first occurrence of a very low value of LDL-C will also be displayed.

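### The SAP's LDL-C conversion factor of 39 does not match its own cut-offs (about 38.67), and the SAP does not say in which unit targets are decided

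*SAP*

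**What the plan says.** SAP 2.5.1 (Lipid formulas) gives one Friedewald formula for results in mmol/L and one for results in mg/dL. After the mg/dL formula it adds: "In order to convert the result into mmol/L, divide by 39".

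The targets in SAP 2.1.3.2 are printed in both units. One key secondary endpoint reads "The proportion of patients reaching calculated LDL-C <70 mg/dL (1.81 mmol/L) at Week 12 (on-treatment estimand"; the companion target pairs 100 mg/dL with 2.59 mmol/L. The very-low definition in SAP 2.4.4.4 is also paired: "A LDL-C level <25 mg/dL (0.65 mmol/L) will be defined as very low", with an alternative cut-off of 15 mg/dL (0.39 mmol/L). SAP 2.1.1 prints baseline LDL-C classes in both units. SAP 2.1.3.2 asks for absolute lipid changes in mg/dL and mmol/L.

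No central laboratory is used: "Total-C, HDL-C, TG will be provided by a local Laboratory". Both reporting units can therefore occur. Neither document says which unit decides target membership or whether values are rounded first.

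Separately, SAP 1.1 gives the group A entry limit as 160 "mg/dL (4.2 mmol/L) despite treatment", where protocol 7.1 has 160 "mg/dL (4.14 mmol/L) despite treatment". For groups B, C and D, SAP 1.1 prints 3.4 mmol/L where the protocol has 3.36.

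**The concern.** The rule that produces mmol/L values and the limits against which such values may be judged were built with different factors. A converted value comes out low relative to the printed mmol/L limit, so a result exactly at a target could pass as below it. The shift runs one way, towards more patients at target in mg/dL laboratories. The same LDL-C could then be classified differently depending on the laboratory's unit. Absolute changes in mmol/L are understated whichever unit decides the targets.

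**Working it through.** **1. Which factor do the SAP's limits imply?** For a pair of m mg/dL and s mmol/L printed to two decimals, the factors that reproduce s run from m/(s + 0.005) to m/(s − 0.005).

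| mg/dL | SAP mmol/L | Factors that reproduce it | m/39 | m/38.67 |
|---|---|---|---|---|
| 15 | 0.39 | 37.98–38.96 | 0.385 | 0.388 |
| 25 | 0.65 | 38.17–38.76 | 0.641 | 0.646 |
| 70 | 1.81 | 38.57–38.78 | 1.795 | 1.810 |
| 100 | 2.59 | 38.54–38.68 | 2.564 | 2.586 |
| 130 | 3.37 | 38.52–38.63 | 3.333 | 3.362 |
| 160 | 4.14 | 38.60–38.69 | 4.103 | 4.138 |
| 190 | 4.91 | 38.66–38.74 | 4.872 | 4.913 |

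A factor of 39 lies outside every range. The ranges for 70, 100, 160 and 190 overlap at about 38.66 to 38.68, so 38.67 reproduces all four; it also reproduces 0.65 and 0.39. It does not reproduce 3.37. It gives 3.36, which is the figure the protocol prints for 130 mg/dL.

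**2. Size of the conversion error.** 1 − 38.67/39 = 0.0085, so converted values are about 0.85% low. As an illustration, a fall of 80 mg/dL is 80/39 = 2.051 mmol/L instead of 80/38.67 = 2.069.

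**3. Percent change.** (x₁₂/39 − x₀/39)/(x₀/39) = (x₁₂ − x₀)/x₀. The factor cancels when it applies to both visits.

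**4. Targets, if applied in mmol/L.** With 39, the printed limits correspond to 1.81 × 39 = 70.59 and 2.59 × 39 = 101.01 mg/dL.

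- 70 mg/dL gives 1.795: counted as below 1.81, rounded or not.
- 71 gives 1.821: not counted.
- 100 gives 2.564: counted as below 2.59, rounded or not.
- 101 gives 2.5897: counted only if unrounded; at two decimals it is 2.59.
- 102 gives 2.615: not counted.
- 25 and 15 mg/dL give 0.641 and 0.385: both counted as very low.

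**5. Targets, if applied in mg/dL.** A mg/dL laboratory result is compared directly with 70 or 100. The factor is not used and no such patient is misclassified.

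**6. Does 38.67 alone cure step 4?** 70 gives 1.8102 and 101 gives 2.6118, both correctly not counted. But 100 gives 2.586, 130 gives 3.362 and 160 gives 4.138; unrounded, these still fall below 2.59, 3.37 and 4.14. Those limits are rounded up, so the deciding unit must also be fixed.

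**7. Share of patients exposed under step 4.** The documents give no Week 12 distribution, so a normal one is assumed. The exposed bands are 70 to 70.59 and 100 to 101.01 mg/dL.

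| Assumed mean/SD (mg/dL) | In 70–70.59 | In 100–101.01 |
|---|---|---|
| 60/35 | 0.64% | 0.59% |
| 80/40 | 0.57% | 0.88% |
| 100/45 | 0.42% | 0.90% |

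If half of the planned 1300 patients (650, also an assumption) used mg/dL laboratories, that is about 3 to 4 patients at the lower target and 4 to 6 at the upper. The overall proportion moves by about 0.2 to 0.45 percentage points. An upper bound comes from assuming that every laboratory reports in mg/dL and that calculated LDL-C takes whole numbers only (mean 60 to 105, SD 30 to 40): 0.7 to 1.3% of patients sit at 70 and 1.1 to 2.6% at 100 or 101.

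**The case against.** The strongest counter-argument is that the SAP may never decide targets in mmol/L. Every target is written in mg/dL first. The LDL-C classes around titration (SAP 2.4.4.2), the very-low flags in the patient listing and the statin subgroup (SAP 2.4.4.4) are in mg/dL only. This stands. A reader might infer that patients at 70 or 100 mg/dL will be counted as at target; the documents do not support that as a certainty. Nor do they settle the opposite. The only stated conversion runs towards mmol/L. SAP 2.4.5.3 converts local laboratory results to the Appendix A units, which are mmol/L for total cholesterol and triglycerides. Protocol 9.1.2 asks for SI units, though in the safety-laboratory section.

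A reader might also infer that mmol/L laboratories are affected in reverse, since 1.80 × 39 = 70.2. The SAP states no such multiplication.

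A third tempting inference is that the 4.2 and 3.4 mmol/L in SAP 1.1 would remove eligible patients from the risk-group subgroups. They would not. SAP 2.4 uses the risk groups at inclusion and says that "enrolled patients who did not fulfill inclusion criterion I 03 will not be considered for this subgroup analysis". Criterion I 03 carries the protocol's 4.14 and 3.36. Although SAP 2.4 points to SAP 1.1 for the groups, that section summarises a classification already made at screening and inclusion, and its mg/dL limits agree with the protocol.

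Finally, the effect is small beside the plan's own precision: SAP Table 1 gives a half-width of 2.7 points at 50% with 1300 patients. For the combined endpoint (below 70 or at least a 50% fall), a patient at 70 mg/dL with a baseline of 140 or more qualifies anyway.

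**Conclusion.** The inconsistency is certain: 39 cannot have produced any of the SAP's paired LDL-C limits. Its certain consequence is that converted mmol/L values, and the size of absolute changes in mmol/L, are about 0.85% too low. Misclassification against the targets is conditional on applying them in mmol/L, a choice the SAP leaves open. If that choice is made, the proportions at target rise slightly, by 0.4 to 0.9% of mg/dL-laboratory patients per target under the three assumed distributions. The study has no hypothesis tests and its primary objective is safety, so no main conclusion depends on this. The SAP 1.1 entry figures are a transcription discrepancy without effect on subgroup membership. This is a small correction, worth making because it is nearly free and removes an ambiguity before programming.

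**What to change.** In SAP 2.5.1, replace 39 by 38.67 and state that it applies to all cholesterol conversions in both directions.

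Add one sentence: membership of LDL-C targets, baseline classes and very-low categories is decided in mg/dL, after conversion at 38.67 where the laboratory reports mmol/L, and the mmol/L figures are labels only. State whether values are rounded before comparison. This matters at the edge: 1.81 × 38.67 = 69.99 is below 70 unrounded, but not when rounded to a whole number.

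As a tidy-up, align the 4.2 and 3.4 mmol/L in SAP 1.1 with the 4.14 and 3.36 in criterion I 03, and the 3.37 label for 130 mg/dL in SAP 2.1.1 and its repeats with 3.36.

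The cost is one constant, one or two sentences and a few printed figures. No data collection changes. Compared with a mmol/L analysis under the present rule, the reported target proportions could be marginally lower.

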## **2.5.2 Data handling conventions for secondary efficacy variables**

See [Section 2.1.3](#).

## **2.5.3 Missing data**

For categorical variables, patients with missing data are not included in calculations of percentages unless otherwise specified. When relevant, the number of patients with missing data is presented.

The analyses and summaries for variables with continuous scales will be based on observed data only. However, the number of patients with missing observations will be provided.

For data listings, the character date will always be used to present the data collected in the CRF.

### ***Handling of computation of age***

Missing birth date conventions:

- missing Day, assume = 15.
- missing Month, assume = 7.
- missing Year, calculations cannot be done.
- Missing Day and Month, assume = 1st of July.

### ***Handling of computation of treatment duration if IMP end of treatment date is missing***

For the calculation of the treatment duration, the date of the last dose of alirocumab is the date of last administration reported on the end-of-treatment case report form page. If this date is missing, the exposure duration should be left as missing.

### ***Handling of medication missing/partial dates***

No imputation of medication start/end dates will be performed. If a medication date is missing or partially missing, so it cannot be determined whether it was taken prior or concomitantly, it will be considered as a prior **and** concomitant medication.

### ***Handling of adverse events with missing or partial date/time of onset***

Missing or partial adverse event onset dates will be imputed so that if the partial AE onset date/time information does not indicate that the AE started prior to treatment, the AE will be classified as treatment-emergent. No imputation of AE end dates/times will be performed. These data imputations are for categorization purpose only and will not be used in listings. No imputation is planned for date/time of AE resolution.

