##### ***Observation period***

For all enrolled patients, the period of safety observation starts from the time when the patient gives his/her informed consent and is divided into the following periods:

- The PRE-TREATMENT observation period is defined from the signed informed consent up to the first dose of alirocumab.
- The treatment-emergent adverse event (TEAE) period is defined as the time from the first injection of alirocumab up to the day of the last injection of alirocumab + 14 days.
- The POST-TREATMENT period will cover a period from the day after the end of the TEAE period up to the end of the study (defined as last protocol-planned visit or the resolution/stabilization of all SAEs and AEs with pre-specified monitoring as defined in protocol).

The on-study observation period is defined as the time from the day of first dose of alirocumab until the last protocol planned visit of the patient.

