##### ***Adverse event observation period***

- Pre-treatment adverse events are AEs that developed or worsened or became serious during the pre-treatment period.
- Treatment-emergent adverse events are AEs that developed or worsened or became serious during the TEAE period.
- Post-treatment adverse events are AEs that developed or worsened or became serious during the post-treatment period.

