#### **2.4.5.1 Analyses of adverse events**

##### ***Generalities***

The primary focus of adverse event reporting will be on TEAEs. Pre-treatment adverse events will be described separately. Likewise, the post-treatment adverse events for the patients concerned (see [Section 2.1.4](#)) will also be described separately.

If an adverse event date/time of onset (occurrence, worsening, or becoming serious) is incomplete, an imputation algorithm will be used to classify the adverse event as pre-treatment or treatment-emergent. The algorithm for imputing date/time of onset will be conservative and will classify an adverse event as treatment emergent unless there is definitive information to determine it is pre-treatment. Details on classification of adverse events with missing or partial onset dates are provided in [Section 2.5.3](#).

Adverse event incidence tables will present by SOC internationally agreed order, HLT, HLT, and PT, sorted in alphabetical order, the number (n) and percentage (%) of patients experiencing an adverse event. Multiple occurrences of the same event in the same patient will be counted only once in the tables within a treatment phase.

For the TEAEs as well as for the pre-treatment adverse events, the denominator for computation of percentages is the safety population. Instead, for the post-treatment adverse events, the denominator will be a sub-group of the safety population (see [Section 2.1.4](#)).

Sorting within tables ensures the same presentation for the set of all adverse events within the observation period (pre-treatment, treatment-emergent, post-treatment). For that purpose, the table of all TEAEs presented by SOC and PT sorted by the internationally agreed SOC order and decreasing frequency of PTs within SOCs will define the presentation order for all other tables unless otherwise specified.

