### ***Analysis of all treatment-emergent adverse events***

The following TEAEs summaries will be generated for the safety population.

- Overview of TEAEs, summarizing number (%) of patients with any
  - Treatment-emergent adverse event,
  - Serious TEAE,
  - Treatment-emergent adverse event leading to death,
  - Treatment-emergent adverse event leading to permanent treatment discontinuation.
- All TEAEs by primary SOC, HLT, HLT, and PT.
- All TEAEs by primary SOC, HLT, HLT, and PT, showing number (%) of patients with at least 1 TEAE sorted by the SOC internationally agreed order. The other levels (HLT, HLT, PT) will be presented in alphabetical order.
- All TEAEs by primary SOC and PT, showing the number (%) of patients with at least 1 TEAE by primary SOC and PT, sorted by the internationally agreed SOC order and by decreasing incidence of PTs within each SOC. This sorting order will be applied to all other tables, unless otherwise specified.
- All TEAEs by PT, showing the number (%) of patients with at least 1 TEAE, sorted by decreasing incidence of PTs.
- All TEAEs regardless of relationship (in one column of the table) and related to alirocumab according to investigator's opinion (in a second column) by primary SOC, HLT, HLT and PT, showing the number (%) of patients with at least 1 TEAE, sorted by the internationally agreed SOC order. The other levels (HLT, HLT, PT) will be presented in alphabetical order.
- All TEAEs by maximal severity, presented by primary SOC and PT, showing the number (%) of patients with at least 1 TEAE by severity (ie, mild, moderate, or severe), sorted by the sorting order defined above.
- The event rate per patient-year (the number of patients with an event in question divided by total patient-years) will be provided for all TEAEs by SOC and PT. For a patient with event, patient year is censored at time of first event; for patient without event, it corresponds to length of TEAE period.
- Kaplan-Meier curves will be provided, when appropriate, for time from first dose of alirocumab to the first occurrence of selected TEAEs as well as incidence rates at 24 weeks of exposure. Patients without any event will be censored at the end of the TEAE period. Selected TEAEs will be all AESIs (as defined in [Section 2.1.4.1](#)).

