### ***Handling of adverse events when date and time of first IMP administration is missing***

When the date of the first alirocumab administration is missing, all AEs that occurred on or after the day of the first dispensation by IVRS should be considered as TEAEs. The exposure duration should be kept as missing.

The last dose administration should be clearly identified in the case report form (on the EOT/EOS page) and should not be approximated by the last returned package date.

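### For AEs with an incomplete onset date, the SAP tests only the pre-treatment boundary, so an event known to start after last injection + 14 days is counted as treatment-emergent

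*SAP*

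**What the plan says.** SAP 2.1.4 divides safety observation into three periods. The TEAE period "is defined as the time from the first injection of alirocumab up to the day of the last injection of alirocumab + 14 days", and the post-treatment period starts the next day. SAP 2.1.4.1 has three matching AE classes, the third being: "Post-treatment adverse events are AEs that developed or worsened or became serious during the post-treatment period". SAP 2.4.5.1 tabulates post-treatment AEs and post-treatment serious AEs separately.

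For incomplete dates the SAP states one rule in two places. SAP 2.5.3 says that "if the partial AE onset date/time information does not indicate that the AE started prior to treatment, the AE will be classified as treatment-emergent". SAP 2.4.5.1 (Generalities) says that "an imputation algorithm will be used to classify the adverse event as pre-treatment or treatment-emergent", and that the algorithm "will classify an adverse event as treatment emergent unless there is definitive information to determine it is pre-treatment". Incomplete onset here covers occurrence, worsening and becoming serious.

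Two further statements bear on the point. When the first-injection date is missing, "all AEs that occurred on or after the day of the first dispensation by IVRS should be considered as TEAEs". On the imputed dates, SAP 2.5.3 adds: "These data imputations are for categorization purpose only and will not be used in listings".

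**The concern.** The classification has two boundaries and the partial-date rule tests one. A recorded month that lies entirely after the TEAE period does not show that the event began before treatment, so the rule returns treatment-emergent. The same SAP's period definitions return post-treatment, and no other section resolves the conflict.

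Safety is the primary objective and SAP 2.4.5.1 puts its main focus on TEAEs. The rule can add such events to the TEAE, serious TEAE and TEAE-leading-to-death tables and take them out of the post-treatment tables. Percentages in the latter use only a subgroup of the safety population, so a lost event weighs more there.

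There is also a smaller gap. The patient-year rate needs a time of first event: "For a patient with event, patient year is censored at time of first event". So do the Kaplan-Meier curves for AESIs and the time to first injection site reaction. The SAP limits imputed dates to categorization and does not say what time a partially dated first event takes in these outputs.

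**Working it through.** **Worked case.** Last injection 10 March 2016. TEAE period ends 10 March + 14 days = 24 March 2016. Ten-week visit: 10 March + 70 days = 19 May 2016. AE onset recorded as May 2016, day unknown.
- By the periods in SAP 2.1.4: every day in May is after 24 March, so the AE is post-treatment.
- By the rule in SAP 2.5.3: May 2016 does not indicate onset before treatment, so the AE is a TEAE.

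**Inputs from the documents.**
- End of TEAE period: last injection + 14 days (SAP 2.1.4). Protocol 11.4.2 words it as + 14 to 21 days; the SAP definition is used here.
- Original protocol, premature discontinuation or switch to another compound: final visit at 10 weeks (SAP 1.5), so 70 - 14 = 56 days beyond the TEAE period.
- Amended protocol: final visit 14-21 days after last injection (Protocol 10.1.2.5), so at most 21 - 14 = 7 days beyond it.
- N = 1300 (SAP 1.3).

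**Assumptions, not in the documents.** Onset uniform over the window; month and year known, day missing; 1-3 AEs per patient-year; 5-10% of AEs with a missing day.

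**Share of post-treatment AEs that month and year alone would identify.** For an onset d days after the TEAE period ends, with the end date uniform within a 30.4-day month, P(later calendar month) = min(1, d/30.4).
- 56-day window: mean = (30.4/2 + (56 - 30.4))/56 = (15.2 + 25.6)/56 = 0.73. Counting every TEAE end date over two calendar years and every onset day from 1 to 56 gives 0.737.
- 7-day window: the same count over days 1 to 7 gives 0.131 (mean day 4, and 4/30.4 = 0.13).

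The remaining AEs share a calendar month with the end of the TEAE period. They are ambiguous and would stay TEAEs under any conservative rule.

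**Events per 100 patients.**
- 56-day window: 100 x 56/365.25 x (1 to 3) = 15 to 46 AEs; x (5% to 10%) x 0.73 = 0.6 to 3.4.
- 7-day window: 100 x 7/365.25 x (1 to 3) = 1.9 to 5.7 AEs; x (5% to 10%) x 0.13 = 0.01 to 0.07. If all 1300 patients were under the amended protocol, this is about 0.2 to 1.0 events in total.

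**Effect on a table row.** 1/1300 = 0.08 percentage points per patient; 5 patients give 0.38 and 13 give 1.0. For comparison, the plan's own interval at a 10% rate reproduces: 1.96 x sqrt(0.1 x 0.9/1300) = 1.6 points, giving [8.4%; 11.6%].

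**The case against.** The strongest defence is one of scope. SAP 2.4.5.1 describes an algorithm for the boundary between pre-treatment and treatment-emergent, so it could be read as leaving the upper boundary to the period definitions. That reading fits 2.4.5.1 taken alone. It does not rescue 2.5.3, which assigns the class outright and has no such limit.

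A second defence is that defaulting to TEAE is a declared conservative choice in a descriptive study. This stands for ambiguous dates and the default should be kept. It does not justify overriding a date known to fall outside the period.

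The size argument also stands. The 73-74% describes only original-protocol patients with the 10-week visit, and the amended protocol leaves little planned time in which the error can occur. Serious AEs and AESIs are reported within 24 hours (Protocol 10.4.3, 10.4.4), so missing days are less likely for them.

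A reader might infer three stronger claims that the documents do not support:
- That all AEs not shown to precede treatment become TEAEs. The rule covers only missing or partial onset dates.
- That the death counts are distorted. Deaths by study period are assigned by when the death occurred or was reported (SAP 2.1.4.2), not by AE onset. Only the table of TEAEs leading to death can be touched.
- That incidence, rate and Kaplan-Meier outputs must disagree for partially dated events. The SAP is silent on event times; it does not state a wrong rule. The Kaplan-Meier curves are limited to AESIs, and the ALT AESI is selected from laboratory data.

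**Conclusion.** The point holds for AEs with a missing or partial onset date. Applied as written, SAP 2.5.3 and 2.4.5.1 give the wrong class whenever the known month or year lies wholly after last injection + 14 days. They do not give a demonstrably wrong class when the month is shared with the end of the TEAE period.

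The practical effect is small and pushes TEAE incidence slightly upward. The shares rest on uniform onset. The event counts rest in addition on assumed AE and missing-day rates, and the size of the 10-week subgroup is not given. The 7-day figure assumes that the planned visit window is kept; the SAP's post-treatment period can run longer while an SAE or AESI is unresolved.

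The correction is still worth making before database lock, because the SAP gives two answers for the same event within its main safety output. The event-time question is a secondary specification gap.

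**What to change.** In SAP 2.5.3, and in matching words in 2.4.5.1, state that an AE with a missing or partial onset date is treatment-emergent unless the known part of the date shows that it started, worsened or became serious either before the first injection (then pre-treatment) or after the day of last injection + 14 days (then post-treatment). Add the same upper limit to the rule for a missing first-injection date. That case should be rare, since the first injection is given at the site under supervision.

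As a secondary clarification, state how partially dated first events are handled in the patient-year rates, the Kaplan-Meier analyses and the time to first injection site reaction. A blanket earliest-compatible-date rule is not advisable: a wholly missing onset would go to the first injection, leaving the patient in the numerator with almost no person-time.

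The cost is two or three sentences and a small programming change, with no new data. The downside is that the TEAE count may fall slightly.
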